Sup	plemer	nts, appendices and other documents	.40
Ap	pendix:	Schedule of events	.41

Key roles

For questions regarding this protocol, contact:

[name] [name], [name] Department of Infant Immunology Vaccinology theme MRC Unit - The Gambia Fajara Tel: Switchboard [name] Mobile: [name] Email: [contact], [contact]

Author:	[name] [name]
Sponsor's representative:	[name]
Principal Investigator(s):	[name] [name]
Investigator(s):	[name]
	[name]
Trial Physician:	[name] [name]
Statistician:	
Data Manager:	??
External Adviser:	[name], [name]
Clinical Laboratory:	
Other institutions:	Imperial College London
	Wellcome Trust UK
Ethics Committee	Gambia Government/MRC Joint Ethics Committee, c/o MRC Unit, The Gambia, [name], The Gambia, West Africa

List of abbreviations

AE	Adverse Event
CRF	Case Report Form
DMC	Data Monitoring Committee
GCP	Good Clinical Practice
ICH	International Conference on Harmonization
IEC	Independent Ethics Committee
MRC	Medical Research Council; represents Medical Research Council Unit, The Gambia
PI	Principal Investigator

Protocol summary

Title:	Group-B streptococci: developing a correlate of protection for future vaccine trials with the help of pregnant Gambian women and their infants	
Brief title:	GBS antibody: developing correlates of protection	
Population:	Pregnant women and Newborn infants followed up until 3 months of age	
Number of participants:	100	
Number of Sites:	1	
Location of Sites:	Faji Kunda Health Centre	
Study Duration:	12 – 15 months	
Duration for Participants:	3 months	
Objectives:	 To describe: 1) To describe the strain-specific prevalence of GBS carriage in women and their infants in a field setting in the Gambia 2) To develop functional tools which enable us to examine the relationship between maternal serotype-specific GBS antibody and carriage of GBS in neonates, which could serve as a surrogate marker for protection from disease in GBS vaccine trials. 	
Description of Study Design:	This longitudinal study will assess mothers and infants at three time points, birth, approx. 1 week and 2-3 months following the birth. A rectovaginal swab, breast milk (1-2mL) and umbilical cord blood sample (4-5mL) will be taken from women in labour and a nasopharyngeal and rectal swab will be taken from the infant at birth. At approx. 1 week a nasopharyngeal and rectal swab will be taken from the infants and breast milk (4-5mL) from the woman. At 2-3	

months a (4-5mL) blood sample will be taken from the infant by venipuncture as well as a nasopharyngeal and rectal swab and (4-5mL) sample of breast milk from the mother. Recruitment will be from the maternity ward at the Faji Kunda health centre, and restricted to healthy singleton infants, birth weight >2.5kg, without congenital abnormalities. Informed consent will be obtained from mothers. 100 pregnant women and their newborn infants will be recruited over 6-months (allowing for a dropout rate of up to 20%).

1 Background information and rationale

1.1 Background information and rationale

GBS Epidemiology

In resource-rich countries GBS is the most common cause of serious bacterial infections in the first week of life (early onset, EO) and of meningitis in the first 3 months of life (late onset, LO), with long-term adverse neurodevelopmental outcomes in up to 30%(1,2). Limited data from three African countries reveal a significant burden of disease (1.21-2.06/1000 live births) including meningitis (4,5,6).

GBS-acquisition occurs through vertical transmission in 15%-50% of infants born to a vaginally/rectally-colonized mother (a prerequisite for EO and risk factor for LO disease)(7,8,9). EOGBS disease can be prevented by intrapartum antibiotics (IAP) and, in a number of resource-rich countries; EOGBS is significantly less common following the introduction of IAP strategies (10,11). However, IAP protection is incomplete and has no impact on LOGBS. In resource-poor countries IAP use poses additional logistical and financial problems and is poorly implemented (12). Maternal vaccination has the greatest potential for preventing invasive neonatal GBS-disease globally.

Although GBS-colonisation is common, few colonized infants subsequently develop invasive disease (estimated 1-2%)(13,14). Despite relatively high maternal carriage rates (22-23%)(15), 13-year old reports have previously shown low invasive GBS-disease rates in the Gambia (16). Possible explanations are: the prevalence of less virulent strains; differing GBS-serotypes, USA/European invasive GBS-serotypes are predominantly serotype-III (17-20) whilst Gambian GBS-serotype studies report serotype-V predominance(21). The difference in invasive disease prevalence could also be due to higher levels of transplacentally-acquired protective antibody; Suara et al. (1998) reported high mean maternal serotype-III antibody levels in women colonised with any GBS-serotype that might account for the rarity of GBS-disease in The Gambia and other resource-poor countries (21). Alternatively, the role of GBS might have been underestimated because of

inadequate culture techniques and microbiological methods (22). In the past six months we have confirmed the predominance of serotype V antibody in pregnant Gambian women and established GBS-invasive disease prevalence of 1.2/1000 live births in a small hospital-based cohort (unpublished data).

A major factor determining differences in GBS-disease incidence is likely due to unrecognized/undetermined causes of neonatal/premature deaths/stillbirths. The majority of deliveries in resource-poor settings occur outside hospital, increasing the probability that infants developing GBS-infection at birth die before infection is reported. Mulholland et al. (1999) excluded neonates dying before day 2 of life - a number of whom may have succumbed to GBS-disease, including meningitis (16). These fatalities would result in inaccurate measures of EO- and LO-disease incidence. The failure to recognize GBS as an important cause of neonatal sepsis in resource-poor countries may therefore reflect insufficient surveillance, true biological population differences or both.

The role of GBS Antibody

To foster effective vaccine development, data describing prevalent serotype differences by geographical region are urgently needed to ensure the inclusion of the most relevant components in a global GBS-vaccine. GBS serotype-specific multivalent CPS-conjugate vaccine candidates, including serotypes Ia, Ib, III and V have been evaluated for safety and immunogenicity in non-pregnant adults(23,24) and pregnant women (25). A major difficulty is the implementation of efficacy trials, which use the prevention of invasive neonatal GBS-disease as endpoint. Surrogate immunological markers, such as protective antibody levels, are required and have previously been used in vaccine licensure, e.g. meningococcal group-C conjugate vaccines.

A protective role for GBS-capsular polysaccharide (CPS) antibodies was predicted in the 1970s(26,27); Infants with invasive EOGBS disease were born to mothers with negligible type-III CPS-specific antibody in sera at delivery. The finding that human sera containing a sufficient concentration of CPS-specific antibody promoted efficient opsonisation and phagocytosis *in-vitro* affirmed the importance of capsular serotype specific antibodies in disease protection. This information suggested that active immunisation of pregnant women with purified GBSCPS could protect young infants (28-30).

GBS antibody in breast milk

Secretory immunoglobulin A (s-IgA), the predominant antibody class in breast milk, plays an important role in maternal-to-infant transfer of immunity in pneumococcal infection and immunization(31) and may also contribute to protection against neonatal GBS-disease(32, 33). Few small studies have assessed the transfer of GBS-antibody in breast milk, demonstrating persistence of serotype-III s-IgA-antibody up to two months of age, indicating their potential role in the prevention or amelioration of LOGBS(33, 34). In a population with a high breastfeeding rate this additional protection against GBS at the mucosal surface plays an important role in immunity from disease.

Data regarding the immunological correlates between maternal serotype, antibody transfer and invasive disease have focused on a limited range of serotypes. To date only one small study of vaccination in pregnant women has demonstrated persistence of serotype-III-antibody in infants up to two months of age (28).

The importance of functional assessments in GBS antibody

In addition to antibody levels, functionality is likely to play an important role. Several killing-based opsonophagocytosis assays (kOPA) that mimic the *in-vivo* process of GBS-killing by host effector cells, following opsonization by specific antibodies have been used for this purpose (35,36). However, bacterial growth, colony plating and counting are time- and resource-consuming steps and standardization presents challenges. Fluorescence-based OPAs (fOPA) can limit these obstacles and development is underway(37,38).In addition, our collaborators at HPA Porton have demonstrated for *Neisseria meningitidis* that antibody-mediated complement C3 deposition correlates strongly with opsonophagocytosis. This assay has advantages of requiring small serum volumes and a large number of sera can be processed in a single assay.

Preliminary data from the Gambia

1.2 Potential risks and benefits

The potential risks to human subjects and known benefits, if any, are summarised in Section "Human Subject Protection".

Improving the health of people of The Gambia

This study will provide much-needed data on prevalence of colonization in mothers and carriage in infants in the Gambia. We wish to provide evidence that any potential vaccine candidates are effective in Gambian women and their infants and will examine the link between maternal carriage, infant colonization and antibody-responses by studying both trans-placental antibody and antibody contained in breast milk. Prospective cohort studies measuring the development of disease in infants born to colonized mothers as an endpoint would have to be extremely large and are beyond the scope of a single-site, resource-limited study. Instead, we will investigate serotypespecific antibody transfer, neonatal antibody persistence and its function in-vitro in order to gain insight into the potential for assays measuring functionally active antibody to be used as a surrogate marker of protection from disease. A functional antibody assay could serve as a surrogate marker for disease for use in vaccine licensure and limit the need for extensive and expensive phase III trials. The main important aspect is that ultimately infants in The Gambia and other resource-poor as well as resource-rich settings can benefit. This represents a long-term aim of course, as we are not conducting a clinical trial but wish to gain deeper insights into mechanisms, which can be exploited for future interventions. We hope that this study will help health professionals to understand more about how maternal immunity can protect infants from GBS disease. We hope that what we find out in this study will help to stop infants in The Gambia and other parts of the world from becoming sick in the future.

Potential benefits to wider communities

This research will contribute to developing methods that require very small blood samples and yet yield a large amount of information through use of flowcytomeric technologies. This will be of benefit not just to my project but also to the wider academic community. I aim to identify serotype

specific antibody to GBS and develop techniques to test the ability of antibody to kill GBS, which could be amenable to industry as a surrogate marker of protection from disease in subsequent phase IV clinical trials. Such correlate markers of protection have already been used in the licensing of meningococcal group C vaccine and have the huge advantage of limiting phase III trial size that often limits vaccine launch.

To examine a possible connection between carriage of organisms and subsequent GBS-antibody concentration and killing ability is a new and evolving area of research, which has become possible through cutting edge flowcytometric techniques allowing the assessment of high sample numbers in a small specimen. This technology is ideally suited to infant serology work. In addition to simply measuring antibody concentration at each time point, we wish to link infant colonisation to functional antibody responses in neonates, which is a novel approach and additionally strengthened by the longitudinal approach within the study, which will swab a number of infants repeatedly.

2 Study objectives

To describe:

- 1) to describe the strain-specific prevalence of GBS carriage in women and their infants in a field setting in the Gambia
- 2) to develop functional tools which enable us to examine the relationship between maternal serotype-specific GBS antibody and carriage of GBS in neonates, which could serve as a surrogate marker for protection from disease in GBS vaccine trials.

2.1 Study endpoints

1. Serotype-specific GBS colonisation in mothers and infants

Prevalence of serotype-specific GBS carriage in mothers and their infants and changes in infant carriage over time will be determined by culturing rectovaginal swabs and infant nasopharyngeal and rectal swabs in selective microbiological media for GBS.

2. Serotype-specific GBS antibody concentration

Serotype-specific GBS antibody-concentration (Ia, Ib, II, III, V) in blood and breast milk will be determined at each of the three time points using flow cytometry.

3. GBS-antibody function

Serotype-specific GBS antibody function (Ia, Ib, II, III, V) will be determined in blood and breast milk using complement C3b/C5 deposition and flow cytometric methods.

3 Study design

3.1 Type of study and design

Study design

Study Design (See Figure 3 for study design).

This is a prospective cohort study, based at Faji Kunda Health Centre of pregnant women recruited at 37 weeks gestation from the antenatal clinic at Faji Kunda and their infants from birth to 3 months of life.

Interventions

- a. Samples in labour: combined rectovaginal swabs will be taken from mothers in labour and nasopharyngeal and rectal swabs their infants at birth. 1mL of colostrum taken within 72 hours of birth, 4-5 mL of cord blood.
- b. Samples at day 6: nasopharyngeal and rectal swabs from infants, 1-2 mL breast milk
- c. Samples at day 56-90: nasopharyngeal and rectal swabs from infants, 4-5 mL breast milk, 2-3mL infant serum

Data Collection

A case report form (CRF) will capture information on:

Epidemiological data:

a) maternal: Site of delivery, mode of delivery, antenatal risk factors for infection (Premature rupture of membranes/chorioamnionitis/maternal fever/raised white cell count), number of live births, information on maternal vaccination status, information of any infections leading up to delivery requiring antibiotics, time in hours of rupture of membranes prior to delivery.

b) infant: gestational age, birth weight, stillbirths/neonatal deaths/perinatal complications

(birth asphyxia/meconium staining/signs of severe infection in the first three months of life (fever >38.5 degrees, raised white cell count, meningism). Gestational age calculated by last menstrual period or midwife palpation or ultrasonography if available.

Sample Collection

- 1) Maternal/infant carriage:
 - a) Maternal swabs: Combined-vaginal-rectal swabs in labor from all mothers who have been consented in the antenatal clinic.
 - b) Infant swabs: nasopharyngeal and rectal swabs in the first 24 hours after birth of all infants whose mothers have been enrolled into the study, second infant swabs on day 6 and final infant swabs collected at day 48

[figure not shown]
2) Antibody Carriage Serum:

[figure not shown]
a) Maternal serum: Cord blood or maternal serum sample at delivery to determine antibody levels.

b) Infant serum: at two months using venipuncture.

3) Antibody Carriage Breast milk:

Breast milk will be collected at day 0, 6 days and 2-3 months post-partum. The women will be given non-sterile surgical gloves and asked to manually express several drops of milk, which were discarded before collecting the specimen directly into the test tube.

All infants will be followed-up from birth to 3 months of age and will receive their EPI schedule normally as shown in Table 1. The flow chart of the study is presented in Figure 7.

 Table 1: EPI Schedule in Faji Kunda

Age (week)	Vaccine
0 (within 48 hours of birth)	BCG, HBV, OPV
8	DTP, Hib, HBV, OPV, PCV-13* RV
12	DTP, Hib, HBV, OPV, PCV-13* RV

*PCV-13 replaces PCV-7 in April 2011.

Key: **BCG**: Bacillus Calmette-Guerin, **HBV**: Hepatitis B vaccine, **OPV**: oral Polio vaccine, **DTP**: Diptheria, Tetanus, Pertussis, **Hib**: *Haemophilus Influenza* Type b, **PCV-13**: Pneumococcal Conjugate Vaccine-13. **RV**: Rotavirus (Rotateq)

4 Selection and withdrawal of participants

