4.1 Selection of participants

Recruitment

Mothers and their newborns will be recruited by MRC Infant Immunology group's field site at Faji Kunda health centre, located in a peri-urban area in The Gambia. Field workers and nurses known to the local community will do sensitization of mothers to the study. Government staff working in the antenatal clinic and on the labour ward at the health centre may provide additional information. When possible, field workers/nurses will talk to potential participants and their families in advance of the delivery to sensitize them to the study and to provide them with a copy of the informed consent document. If a pregnant woman is interested in the study, a sticker will be placed in her yellow antenatal record card. She will also be given a card with contact numbers for the study staff. The study team will be contacted when women present in labour either by the women themselves, or the midwives on duty. Mothers presenting to the health centre in labour

may additionally be sensitized to the study if this has not occurred in advance and when adequate time is available.

Oral consent will be gained from the mothers at the time of delivery in order to collect rectovaginal swabs before delivery and cord blood (which has to be processed within 6 hours of collection). The midwives will collect cord blood samples on duty or by a member of the study team. Written informed consent will then be obtained by a fieldworker/nurse shortly after birth, when they have recovered sufficiently and will include consent to collect a nasopharyngeal and rectal swab from the newborn and to collect breast milk. Final enrolment will occur after informed consent has been obtained and only if the neonate meets the inclusion criteria and does not meet any of the exclusion criteria (see below).

They will be asked to provide further informed consent to a nasopharyngeal and rectal swab of the newborn and collection of breast milk coinciding with the first postnatal check at approximately 6 days post-partum. A Final breast milk sample, infant venipuncture sample and nasopharyngeal and rectal swab will be taken at 2 months at the infant's first immunisation clinic visit.

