5.2.2 Laboratory evaluations

Swab culture

Rectovaginal swabs will be taken from all mothers at presentation in labour and sent same day to the MRC laboratory. Nasopharyngeal and rectal swabs will be taken from all infants and sent same day to the MRC laboratory. Maternal and infant swabs will be pre-cultured overnight in Todd Hewitt Broth and cultured by plating on selective blood agar plates for 48 hours. If there is any bacterial growth this will be identified as GBS by latex agglutination test and serotyping by RT-PCR.

Cord blood and at 2 to 3-months of age

Additional experiments will be done from the cord blood samples and from the infants at 3-months of age in order to complete the antibody aspect of this study. The blood samples will need to be transported to MRC laboratories in EDTA tubes within 6 hours of collection, spun down and frozen at -70 degrees. The samples will be batched and sent to Porton Down, UK for serotype-specific antibody analysis and complement deposition studies.

Breast milk

Additional experiments will be done from breast milk samples collected at birth, day 6 and day 60. Women will be asked to hand express 1-2mL of colostrum at the first visit and 4-5mL of breast milk on day 6 and day 60. Breast milk should be expressed from each breast and collected in two sterile universal containers. The samples need to go immediately into cold storage and transferred same day to the laboratory. The samples then need to be aliquoted into 100uL samples and frozen at -70 degrees. Batches of breast milk will then be sent to Porton Down for antibody analysis and complement deposition studies.

Sample handling Cord blood and 3 months

Spin sample, take off serum into two aliquots and PLACE SAMPLE STRAIGHT IN -70°C & RECORD LOCATION IN WORKSHEETS

Table 2 - Laboratory experiments

Experiment	Time course	Volume required	Method	Sample storage
1. Microbiological swab culture	48 hours (12-56 hours)	1 combined rectovaginal swab (mother) 1 nasopharyngeal swab, 1 rectal swab (infant)	See SOP	Store at 4 degrees until culture. Culture at 37 degrees
2. Antibody surface labeling studies	4 hrs (3.5- 4.5 hrs)	>2mL	See SOP	Serum in YELLOW tubes, spin down and aliquot into 2 aliquots and store at -70°C

3. Complement deposition studies	4 hrs (3.5- 4.5 hrs)	>2mL	See SOP	Serum in YELLOW tubes, spin
· ·	4.5 hrs)			
studies				down and
				aliquot into 2
				aliquots and
				store at -70°C

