Formal analysis will be based on linear regression for each serotype and will test whether maternal antibodies predict colonization in newborns. Antibody responses will be suitably transformed to satisfy the normality and constant variance assumptions for the regression based analyses. As the relationships are likely to be non-linear fractional polynomials will be used to model non-linearity. In addition to analyses based on continuous data, responses will be categorized and contrasts used to make appropriate comparisons. Where possible regression will be adjusted for potential confounders including mothers with high levels of carriage who have not yet mounted an antibody response, infants without antibody and maternal and infant infections. With both maternal and infant longitudinal sampling, separate analyses will be repeated at each time point. Discrete analyses

based on carriage will be analyzed using a survival analysis approach. With multiple time points and multiple serotypes from the same subjects, false discovery rates will be used to control for false positives from multiple hypothesis tests.

8 Data handling and record keeping

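### The timing of the only infant venous sample is contradictory, and if the full day 56-90 window is used, final-visit infant antibody results are mixed with infant age

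*Protocol*

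**What the plan says.** The infant has one venous sample, at the last visit. Its timing is given in these places:

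- Protocol summary: at 2-3 "months a (4-5mL) blood sample will be taken from the infant by venipuncture".
- Section 3.1, Interventions: "Samples at day 56-90: nasopharyngeal and rectal swabs from infants, 4-5 mL breast milk, 2-3mL infant serum".
- Section 3.1, Sample Collection: "Infant serum: at two months using venipuncture".
- Section 4.1: the sample "will be taken at 2 months at the infant's first immunisation clinic visit".
- Section 5.2.2: a heading gives 2 to 3 months, but the text beneath it has samples "from the infants at 3-months of age in order to complete the antibody aspect of this study".

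The companion samples at that visit disagree as well. The Sample Collection list in Section 3.1 puts the final infant swabs at day 48, while Interventions in the same section includes them in the day 56-90 window. Section 5.2.2 puts the last breast milk sample at day 60.

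On analysis, Section 7 states that "separate analyses will be repeated at each time point". It adjusts where possible for an open list of confounders. Those named are mothers with high carriage and no antibody response yet, infants without antibody, and infections. Age at sampling is not among them.

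Section 1.2 says the study will look at how long antibody lasts in the infant and how it functions. Section 2.1 makes antibody concentration and function in blood endpoints.

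**The concern.** This one sample carries all the infant serum evidence on how maternal antibody lasts after birth. Antibody acquired before birth declines with age, so a level at two months and a level at three months are different quantities. The protocol's own background treats infant antibody as age-dependent: it cites persistence to two months in an earlier vaccination study, and it reports a rise between 24 and 56 weeks.

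Staff working from Section 4.1 and staff working from the laboratory text could bleed infants about a month apart, and both samples would enter the analysis as the same time point. An infant bled late would then look like one with poor persistence. Section 7 also plans to categorise responses, and a fall due only to age can move an infant across a cut-off. If age at bleed is unrelated to everything else, the result is added noise. If late attendance goes with illness or carriage, it becomes bias. The documents do not say which applies.

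**Working it through.** **No stated figure.** The protocol gives no calculation on this point, so there is nothing to reproduce. The check is calendar arithmetic plus a sensitivity calculation.

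**Width of the window (Section 3.1).** 90 - 56 = 34 days, or 35 possible sampling days.

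**Timings side by side.**

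| Place | Last infant blood |
|---|---|
| Protocol summary | 2-3 months |
| Section 3.1, Interventions | day 56-90 |
| Section 3.1, Sample Collection | two months |
| Section 4.1 | two months, first immunisation visit (week 8 in Table 1; 8 x 7 = day 56) |
| Section 5.2.2, heading | 2 to 3 months |
| Section 5.2.2, text | 3 months |

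The broad window can contain the two-month and three-month statements, but those two cannot both be the plan. The day 48 swab lies 56 - 48 = 8 days before the window opens. If it were followed while blood was drawn at day 56-90, swab and serum from the same visit would be 8 to 42 days apart (90 - 48 = 42).

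**Fall from age alone.** The documents give no half-life h for maternal antibody in the infant, so 20 to 45 days is assumed. Fold fall across the window = 2^(34/h).

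If bleed days were spread evenly over the window (also an assumption), the standard deviation that age adds on the natural-log scale is (ln 2 / h) x 34/√12.

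| Assumed half-life | Fold fall, day 56 to 90 | Log-scale SD from age |
|---|---|---|
| 20 days | 3.25 | 0.34 |
| 30 days | 2.19 | 0.23 |
| 45 days | 1.69 | 0.15 |

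**Share of total variance.** Assume a between-infant log-scale SD of 0.8 to 1.6, which is not in the documents either.

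- Largest: 0.34² / (0.34² + 0.8²) = 0.15.
- Smallest: 0.15² / (0.15² + 1.6²) = 0.009.

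Age would account for about 1% to 15% of the spread.

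**If bleeds stay close to the Section 4.1 timing.** Taking day 56 to 60 as an illustration, the span is 4 days. The fold fall is 2^(4/20) = 1.15 to 2^(4/45) = 1.06, so most of the age effect disappears.

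**The case against.** Two of the statements, including the most specific one in Section 4.1, point to two months. On that reading day 56-90 is only an outer limit and the age spread is small. The confounder list in Section 7 is open, and a separate analysis plan, which is not among the documents, may name age. Two- to three-fold compares the extremes of the window, and as a share of variance age is modest. The formal regression uses maternal antibody to predict newborn colonisation, so this sample is not its predictor. All of this stands, and it limits the size and reach of the point. It does not remove the contradiction, which is in the protocol's own text: the laboratory section says three months, and the summary and Section 3.1 allow it.

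A reader might go further and infer that routine vaccination confounds the result. Table 1 lists "DTP, Hib, HBV, OPV, PCV-13* RV" at weeks 8 and 12, which are days 56 and 84 (12 x 7). Both lie in the window. With vaccines on schedule, 27 of the 35 days follow one round and 7 fall at or after the second. The documents do not support the inference. None of the listed vaccines targets GBS, the endpoints are GBS serotype-specific, and no effect on these assays is stated. Nor could a bleed follow two of these rounds if it is taken at the first immunisation visit.

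A reader might also infer that a cord-to-infant persistence ratio is distorted. The protocol defines no such ratio.

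**Conclusion.** The point holds in a limited form. The protocol contradicts itself on when its only infant venous sample is taken, and on when the companion swabs are taken. If the full 34-day window is used, analysing the visit as one time point mixes infant antibody concentration and function with age. The size is about 1.7- to 3.3-fold between the ends of the window, on an assumed half-life of 20 to 45 days, and small if the Section 4.1 timing is followed.

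The effect is confined to results from final-visit infant serum. Maternal or cord antibody against newborn colonisation is not affected, and no vaccine effect on GBS antibody can be claimed from the documents. Bias, as opposed to added noise, would need late attendance to be related to antibody or carriage, which the documents do not show.

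**What to change.** Reconcile the Protocol summary and Sections 3.1, 4.1 and 5.2.2 on when the final infant blood and swabs are taken, including the day 48 entry. Which timing to adopt is for the investigators.

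In Section 7, state that analyses of final-visit infant serum include exact age in days at the bleed as a covariate. The number of routine vaccine rounds received can be described from the vaccine details that Section 5.2.1 already records. It need not be a covariate, and persistence need not be recast as a daily decay rate.

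The cost is a change of wording, plus making sure that the visit date is recorded on the case report form, which the protocol implies but does not list. The statistical price is one extra covariate in a small data set: the Protocol summary plans 100 pairs with up to 20% drop-out, so about 100 x 0.8 = 80 at the last visit.
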